- k. Certain data elements are transformed during transfer from paper to electronic (e.g. birthdate to age, subject start and end date to time of participation). However, it is will always be possible if necessary to compare the original data and observations with the processed data.
- l. The subject code used in the electronic database is an unambiguous random number that allows identification of all the data reported for each subject. The code is not related to any HIPAA element.
- m. It is understood that CAVHS and the VA have ownership of all data.
- n. The study will purchase the investigational products from a VA-authorized vendor and have them shipped directly to the VA pharmacy. The pharmacy will maintain accountability for receipt, storage, and dispense of these products as described in the clinical trial product information sheet. The pharmacy and study monitor will also maintain accountability for return of unused investigational products.

LABORATORY ASPECTS OF THE STUDY

Study Outcomes: The study will examine the effects of the nutritional supplement on measures of immune function and muscle health. The immune response to three types of stimulation will be measured: antibody response to vaccination, immune response in muscle and blood to a bout of exercise, and an in vitro response for immune cell proliferation. Muscle adaptation to training will be measured at the whole body (i.e. muscle cross-sectional area, strength, and function) and cellular levels. The blood and muscle tissue collected from the subjects at the described time points will be used for laboratory analyses of variables related to immune function and muscle adaptation to exercise training. The basis for the expectations that each measure will be affected by the ingredients of the nutritional supplement (β -hydroxy- β -methylbutyrate, arginine, and glutamine) and/or resistance exercise is provided.

The specific proposed method of measurement or measure of immune function (and associated hypothesis) in muscle or blood may change for practical and scientific reasons and not be considered a deviation so long as the measure: 1) addresses a molecular or cellular trait potentially impacted by aging and muscle health or the improvements of muscle health by supplementation or exercise; 2) is not genetic testing; 3) and the results will not be communicated back to the subjects or used to influence their medical care in any way.

BLOOD MEASURES

- A. **Response to Vaccination:** β -hydroxy- β -methylbutyrate has been used in animal science to improve the response to vaccination [32]. The study will determine if 2-weeks of supplementation improves the response of older adults to the TDAP vaccine. The response to *pertussis* is of primary interest though the responses to the tetanus and diphtheria antigens will also be measured. Serum antibody titers will be compared between pre-vaccination and two time points post-vaccination. Enzyme-linked immunosorbent assays are available for measuring antibodies to each antigen (IBL International, Toronto, Ontario).
- B. **T-Cell Subpopulations:** Glutamine and arginine may be conditionally essential amino acids in the contexts of aging and exercise that are needed for optimal T-Cell function [34;56]. Aging decreases the ratio of naïve helper (CD4+) to cytotoxic (CD8+) T-Cells [57]; and though the levels of both cell populations increase shortly after moderate exercise for older adults, their levels do not reach the pre-exercise levels of young adults [58]. The proposed study will determine if 2-weeks of supplementation increases the CD4+ to CD8+ ratio or increases the response to acute exercise. A regulatory t-cell subset (CD4+, CD25+, FoxP3+) will also be examined since these cells function as regulators of immune function that prevent an uncontrolled immune response or autoimmunity [59]. Assessment of T-cell subsets will be carried out by flow cytometry using fluorochrome-linked antibodies specific to each marker (BD Biosciences, San Jose, CA). Additionally, if an alteration in inflammatory status is indicated by the cytokine analysis, then the Th17 subset (CD4+, CCR6+, CD161+, ROR α +) will be evaluated. This pro-inflammatory subset has not been studied following supplementation or exercise and the results could provide for the first time information on whether alteration in Th17 t-cells accompanies improvement in immune status.
- C. **Cytokine and Chemokines:** Immune responses are either predominated by pro-inflammatory Th1 cytokines (e.g. IFN- γ , TNF- α , IL-2, and IL-17) or anti-inflammatory Th2 cytokines (e.g. IL-10 and IL-4) and chemokines depending on the nature of the stimulus. However, arginine and glutamine may be able to limit the production of these factors [36]. Since aging is thought to increase basal cytokine levels and impair the cytokine response to exercise [60], the study will determine if 2-weeks of supplementation decreases baseline cytokine levels and increases the response to acute exercise. Cytokines and chemokines will be measured using the multiplex Luminex array system (Bio-Rad, Hercules, CA) and confirmed using high sensitivity enzyme linked immunosorbent assays (R&D Systems, Minneapolis, MN).
- D. **Immune Cell Proliferation:** In vitro models indicate that glutamine and arginine are important to immune cell proliferation [34;61]. Similarly, human trials of β -hydroxy- β -methylbutyrate, arginine, and glutamine have shown that monocytes, lymphocytes, and T-cells increase after treatment [27;46]. Proliferative capacity of lymphocytes also increases shortly after moderate exercise but the change is significant only in young and not older adults [58]. This study will determine if 2-weeks of supplementation increases the in vitro proliferative capacity of peripheral blood mononuclear cells at either baseline or after acute resistance exercise. After the in vivo effect of the supplement is determined, the results will be confirmed using the supplement or its individual ingredients to treat cells in vitro. Proliferation will be measured by flow cytometry based on uptake of a fluorescent dye (carboxyfluorescein succinimidyl ester) after treatment with phorbol ester and calcium ionophore as was used in Finding 5.

MUSCLE MEASURES

- E. **Macrophages:** Evidence from animal models indicates that arginine and glutamine metabolism is involved with macrophage activation that mediates inflammation or anti-inflammation and growth [35;37]. Our preliminary results indicate that the majority of macrophages residing in muscle perform the latter of these two functions, i.e. anti-inflammation and growth. However, muscle of

older adults contains fewer macrophages and the numbers do not increase in response to acute exercise. The study will determine if 2-weeks of supplementation increases the number of macrophages present in muscle at baseline or in response to acute resistance exercise. Macrophages will be counted in muscle cross section by immunohistochemistry using antibodies to detect the CD163 marker (Cell Sciences, Canton, MA). Additional markers (CD68 and CD206) will be used to confirm the specificity of the CD163 marker to macrophages.

F. Cytokines and Growth Factors: Our preliminary results show that older muscle contains elevated basal levels of cytokines and diminished levels of growth factors. The effect of arginine and glutamine on cytokine expression is expected to be the same in tissue as it is systemically. The study will determine if 2-weeks of supplementation decreases baseline cytokine levels and increases the response to exercise. Since chronic inflammation is thought to dampen growth factor production [62], the study will determine if supplementation also increases growth factor levels at baseline and in response to exercise. IL1 β , IL10, and IGF1 are of primary interest though the other cytokines, and growth and remodeling factors *including MuRF and MAFbx* which will also be measured. Gene expression will be measured at the mRNA level using total RNA extracted from whole muscle by quantitative real-time PCR. Assays will utilize SYBR green chemistry and standard curves as was used in Findings 1-4 (Figures 2-5).

G. Nuclear Factor- κ B (NF κ B) and Phosphatidylinositol 3-Kinase Signaling (PI3K): Direct assessment of protein and protein activity in human muscle has proven difficult for cytokines and growth factors including IGF1, one of the most commonly studied regulators of muscle mass. For this reason, the study will evaluate muscle for cytokine (NF κ B) and growth factor (PI3K) activity by evaluating signal transduction pathways involved in regulation of muscle hypertrophy and atrophy [63]. The study will determine if 2-weeks of supplementation decreases NF κ B signaling and increases PI3K signaling at baseline and in response to exercise. NF κ B activity will be assessed by electrophoresis mobility shift assays to detect muscle nuclear protein binding to the NF κ B DNA site as used in Figure 9A or as follows for PI3K. PI3K activity will be assessed by Western Blot based phosphorylation assays (Millipore, Billerica, MA).

H. Additional Signaling Pathway Members: The regulation of inflammation and growth in macrophages and muscle cells is regulated by a complex network of signaling molecules. Thus, in addition to NF κ B and PI3K, other factors will also be measured for effects of supplementation and exercise [24;25;64]. Of main interest are FOXO1, STAT3, AKT, S6K, and ERK1 and 2. The activity of these factors is regulated, in part, by their phosphorylation state. Matched antibody pairs are available to measure the ratio of these phosphorylated to un-phosphorylated proteins by Western Blot (Cell Signaling Technology, Boston, MA). Pathway scanning kits are also available which include other related molecules in the cascade. Muscle remains from the nutritional supplement pilot study presented in the introduction. This muscle will enable an initial broad assessment of the signaling pathways affected by nutritional supplementation. The results will guide any changes in the specific factors chosen for assay in muscle collected for the proposed study.

I. Satellite Cells and Myonuclei: Muscle adapts to resistance training through increases in satellite cell numbers and addition of nuclei to the myofiber [21]. However, these adaptations are diminished in older adults [22]. The study will determine if 15-weeks of supplementation increases the number of satellite cells and myonuclei per myofiber in muscle. Satellite cells (Pax7+, CD56+, DAPI+) and myonuclei (Dystrophin plus DAPI staining) will be counted using established staining methods [21].

J. Fiber Size: Muscle also adapts to resistance training by muscle fiber hypertrophy. However, this growth is hindered in individuals, particularly older adults, who have a diminished satellite cell and myonuclei response to training [22]. The study will determine if 15-weeks of supplementation increases the effects of resistance training on myofiber size. Changes in fiber size will be

measured microscopically as the average percent increase in fiber cross-sectional area from baseline to post-training.

STATISTICAL PLAN: The sample size (N=50) provides greater than 80% power for Aims 1-3 to detect mean differences between groups of 0.8 to 0.85 standard deviation (SD) units at a 5% level of significance. Power calculations were based on using a one-sided t-test to compare independent groups using data from our work and others [2;23;65] though non-parametric tests or transformations will be used as necessary for data containing outliers. There is no formal plan to adjust for multiple comparisons. However, multiple correlation analysis will be used to determine the correlation between endpoints and any possible inflation in the overall Type I error rate. This analysis will allow testing of the overall hypothesis that measures of immune function (Aim 1) will be positively correlated with adaptations to exercise (Aim 2) and retention of muscle strength, mass, and function after exercise training is halted (Aim 3). The hypotheses are stated for each aim and the time points for comparison are listed in Table 6.

Aim 1 Power: Aim 1 will determine if the supplement consumption for 2-weeks improves baseline measures of immune function or the immune responses to vaccination or acute exercise. The representative measures chosen to calculate power are change in muscle macrophage content after exercise (Finding 2) and change in CRP levels post-supplementation (Pilot Study Finding 1). Przybyla et al detected a 29% increase in CD163+ macrophages in young subjects after exercise but no change in older subjects [2]. Power for this aim is calculated to detect at least a 29% greater increase in macrophages in the supplement than the placebo group. Przybyla et al used a nonparametric test to lessen the effects of outliers. To be more conservative here, the calculations here dropped the most extreme high and low data values before estimating effect sizes. With that approach, the 29% increase corresponds to an effect size of 0.8 SD units (mean/SD = 0.128/0.159). Similar results were found using CRP data from Pilot Finding 1. The effect size for change in CRP is 0.85 SD units (mean/SD = 0.665/0.780 for log-transformed data). Having at least 20 subjects per group will provide 80% or greater power to detect a mean shift of 0.8-0.85 SD units at a significance level of 5% for the following Aim 1 hypotheses:

- a. The response to vaccination will be greater in the supplement than the placebo group. The change between times K and A (Table 6) will be compared between groups.
- b. The resting ratio of CD4+ to CD8+ t-cells will increase in the supplement but not in the placebo group. The change between times G and C will be compared between groups.
- c. The change in t-cell subsets after acute exercise will be greater in the supplement than the placebo group. The change between times I and G will be compared to the change between times E and C for both groups.
- d. Resting cytokine levels will decrease in the supplement but not in the placebo group. Change will be compared between groups for blood (times G and C) and muscle (times H and D). *Similar results are predicted for the MuRF and MAFbx atrophy-related transcripts.*
- e. The increase in cytokine levels after acute exercise will be greater in the placebo group than the supplement group. For both groups, change between times I and G will be compared to the change

Table 6. Time points are lettered for clear reference by the stated hypotheses.	
BASELINE MEASURES (WEEKS 1-5)	
A.	Blood draw at study enrollment for measuring pre-vaccination antibody titers
B.	Assessment of muscle strength, mass, and function at baseline
C.	Blood drawn prior to acute exercise at baseline
D.	Muscle biopsy prior to acute exercise at baseline
E.	Blood drawn 1 hr after acute exercise at baseline
F.	Muscle biopsy 72 hrs after acute exercise at baseline
POST-SUPPLEMENT RUN-IN MEASURES (WEEK 8)	
G.	Blood drawn prior to acute exercise after 2-weeks of supplementation
H.	Muscle biopsy prior to acute exercise after 2-weeks of supplementation
I.	Blood drawn 1 hr after acute exercise after 2-weeks of supplementation
J.	Muscle biopsy 72 hrs after acute exercise after 2-weeks of supplementation
MEASURES DURING TRAINING PERIOD (WEEKS 9-20)	
K.	Blood draws at weeks 1 and 2 post-vaccination for measuring antibody response
POST-TRAINING MEASURES (WEEK 21)	
L.	Assessment of muscle strength, mass, and function after completion of training
M.	Muscle biopsy 72 hrs after final exercise bout of training
MEASURES DURING POST-TRAINING FOLLOW-UP (WEEKS 22-4)	
N.	Assessments of strength, mass, and function after 16 and 26 weeks of detraining

between E and C for blood, and for muscle the change between times J and H will be compared to the change between times F and D.

- f. The proliferative capacity of peripheral blood mononuclear cells will be greater in the supplement than the placebo group. The change between times G and C will be compared between groups. The change between times I and E will also be compared between groups.
- g. The resting number of muscle CD163+ macrophages will increase in the supplement but not in the placebo group. The change between times H and D will be compared between groups.
- h. The number of muscle CD163+ macrophages will increase after acute exercise in the supplement but not in the placebo group. The change between times J and H will be compared to change between times F and D for both groups.
- i. Resting NFkB activity will decrease and PI3K activity will increase in the supplement group but not in the placebo group. The change between time points H and D will be compared between groups.
- j. In response to acute exercise, NFkB activity will be lower and PI3K activity will be greater in the supplement group than in the placebo group. The change between times J and H will be compared to change between times F and D for both groups. *Responses similar to NFkB are predicted for FOXO1, and responses similar to PI3K are expected for STAT3, AKT, P38 MAPK, and ERK 1 and 2.*

Aim 2 Power: Aim 2 will determine whether supplement consumption increases muscle adaptation to 12-weeks of resistance training. The representative response measure for this objective is post-training percent increase in muscle strength. In a similar study, Trappe et al sought to improve strength gain by resistance training plus drug treatment. The drug treatment group gained significantly more strength by 25.1% than the group receiving placebo (26.4% vs. 21.1%, $P<0.05$) [23]. The previous findings presented here (Finding 4) indicate that older subjects completing a 12-week training program but not taking supplements will experience an average strength gain of $25 \pm 8\%$. If treatment with the proposed supplement improves strength similarly to the Trappe drug treatment, subjects in the supplement group will improve strength by an average of 31% (i.e., 25.1% greater than those of the placebo group). This translates to an approximate effect size of 0.8 SD units ($0.25*0.251/0.08$) if variances are pooled for the groups compared. With 20 subjects per group, there will be 80% power to detect a mean shift of 0.8 SD units using a significance level of 5% for the Aim 2 hypotheses:

- a. The amount of strength gained from 12-weeks of training will be greater in the supplement than the placebo group. The change between times L and B will be compared between groups.
- b. The amount of muscle size gained from 12-weeks of training will be greater in the supplement than the placebo group. The change between times L and B will be compared between groups.
- c. The increase in muscle function after 12-weeks of training will be greater in the supplement than the placebo group. The change between times L and B will be compared between groups.
- d. The increase in muscle satellite cells after 12-weeks of training will be greater in the supplement than the placebo group. The change between times M and D will be compared between groups.
- e. The increase in muscle myonuclei after 12-weeks of training will be greater in the supplement than the placebo group. The change between times M and D will be compared between groups.
- f. The increase in muscle fiber size after 12-weeks of training will be greater in the supplement group than the placebo group. The change between times M and D will be compared between groups.

Aim 3 Power: Aim 3 will determine if supplement consumption increases the retention of exercise-derived benefits post-training during 26 weeks of long-term follow-up. The representative response measure for this objective is the strength gain retained during long-term follow-up after exercise training is completed. Lemmer et al observed an average gain in muscle strength of 27% ($P<0.01$) in older men after strength training which is similar the 25% gain presented here in Finding 4 [65]. However, at

31-weeks of post-training follow-up, strength had decreased to be about 9% above pre-training levels. Assuming the same level of variation among our subjects in retention of strength gain as the observed 8% SD for strength gain in Finding 4, then a 0.8 SD effect size would be about 6.4% ($0.8*0.08$), translating to our supplement group retaining strength of 12.4% above pre-training levels. With 20 subjects per group, there will be 80% power to detect a mean shift of 0.8 SD units using a significance level of 5%. If the SD for retention of strength is smaller than 8%, then we will have higher power to detect the same difference or equal power to detect smaller differences for the following Aim 3 hypotheses:

- a. The change in strength during the detraining period will be smaller in the supplement than the placebo group. The change between times N and L will be compared between groups.
- b. The change in muscle size during the detraining period will be smaller in the supplement than the placebo group. The change between times N and L will be compared between groups.
- c. The change in muscle function will be smaller in the supplement than the placebo group. The change between times N and L will be compared between groups.

Reference List

4. Ellis A. Dietary Supplements and Aging Muscle. University of Alabama at Birmingham and the National Center for Complementary and Alternative Medicine (NCCAM) [2012 Available from: URL:<http://www.clinicaltrials.gov/ct2/results?term=NCT01057082>

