Objective: The study will examine the influence of immune function in older adults on improvement of muscle mass, strength, and function by resistance training. The maintenance of those benefits during long term follow-up will also be examined. This objective will be accomplished by a double-blind randomized placebo-controlled trial of a nutritional supplement (Muscle Armor) which evidence suggests can improve immune function, promote muscle growth, and counteract muscle loss. The study premise is that aging results in decreased ability of the immune system to respond to stimuli such as exercise. The study proposes that the supplement will improve muscle health by promoting a shift in immune function of older adults from a pro-inflammatory state towards a state which supports muscle growth and maintenance.

Research Plan: The study will randomize veterans (age 60-80, N=50) to participate in the supplement or placebo groups in a three phase study. The phases of participation correspond to the three specific aims. Aim 1 will determine if 2-weeks of supplementation improves immune function. Humoral immune function will be assessed as the response to vaccination. Innate immune function will be measured as systemic and cellular responses to acute resistance exercise that our previous studies indicate are affected by aging. Aim 2 will determine if supplementation during 36 sessions of progressive high-intensity resistance training boosts improvement in muscle size (CT scan), strength, and function (gait and balance). Muscle adaptations at the cellular levels will also be measured. Aim 3 will determine if continued supplementation for 26-weeks after completion of exercise training promotes the retention of the gains in muscle size, strength, and function. Multivariable testing will then be used to compare the results between Aims 1, 2, and 3 to determine whether or not immune function is correlated with muscle adaptation to training or detraining.

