Results and Conclusions for Vaccination: The results for the antibody response to the pertussis antigen are shown in Figure 8. Median levels of antibody increased in both groups after vaccination. The increase from pre-vaccination was greater in the supplement than the placebo group at both 1-week (37.8 v. 19.6) and 2-weeks (131.0 v. 70.7) post-vaccination. Based on a Mann-Whitney test, the difference between groups in the 2-week change in pertussis antibody titers was not statistically significant ($P=0.13$). Thus, it is unknown whether the proposed sample size ($N=50$ with 20% dropout) will allow detection of differences between supplement and placebo groups though the nonparametric test result based on only $N=12$ is suggestive that it may. Regardless, the measure remains valuable to the study because it is a good general measure of immune function that is quite variable for older adults. This variability is amenable to planned within group analyses to determine the correlation between immune function and muscle adaptation to training and detraining. This issue was previously addressed in the pitfalls section of the proposal is reiterated here due to its importance. The aims were purposefully designed to be independent so that conclusions can still be drawn for the relationships between immune function and training outcomes as well as supplementation and training outcomes even if immune function is not altered by supplementation.

[figure not shown]

Figure 7. Change in CRP levels after 4-weeks of consumption of Muscle Armor or placebo. Mean and standard error of change are shown.

[figure not shown]

Figure 8. Effects of Muscle Armor or placebo consumption on median response to the pertussis vaccine at 1- and 2-weeks post-vaccination.

RESEARCH DESIGN & METHODS

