- b. Use of Certain Medications: it is unknown how certain medications (specifically those used to control inflammation) and other age-associated medical issues will influence the variables of interest to the study. Due to this possibility, medications and medical problems will be recorded and used as potential confounding variables in the statistical or exploratory analyses.

15. Computed Tomography Scan of the Thigh

- a. **Procedure:** Muscle Cross-Sectional Area and composition will be determined by the hospital imaging service using computed tomography (CT) scan of the mid-thigh at pre-training, post-training, and at the end of the study. The service performed CT scans for our previous study which showed that size increased ($P=0.002$, $7.4 \pm 2.0\%$) in older adults after 12-weeks of

training [3]. Subjects are carefully positioned in the scanner and boney land marks are used to ensure precise mid-thigh location for each scan. Analysis of scans will be completed using a program such as Slice-O-matic (Montreal, Canada) to discern between bone, fat, and muscle.

CT scan data is transferred from the Imaging service to the study on a CD which is not encrypted per se. However, the risk of an unintended recipient accessing the data is particularly low because specialized software is required to view the data. Furthermore, the data is a cross-sectional image of the thigh which looks like a slice of ham (i.e. not sensitive). The information will be labeled with the subject study ID, not name or SSN. Transport of the disk from the LR to NLR VA will occur in a locked bag and the disks will be maintained according to CAVHS regulations.

- b. **Benefit:** The CT scan of the thigh is of no direct benefit to the subject though the measure provides important scientific knowledge of the effects of exercise training, detraining, and nutritional supplementation in older adults.
- c. **Risk:** The procedure will expose subjects to radiation. The total amount of radiation the subjects will be exposed to per scan (6 mSv) is approximately the same as the average exposure an individual has from natural sources per year. Having three scans in one year creates a very small increase (from 44.9% to 44.95%) in the risk of cancer for the average 70 year old male (www.xrayrisk.com).

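### The plan does not say how treatment arm enters the immune-muscle correlation; one arm-adjusted model in all subjects would be more precise than separate within-arm correlations and would rule out confounding by arm

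*Combined protocol and SAP*

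**What the plan says.** The link between immune function and muscle outcomes is one of the four key questions listed at the front of the protocol. Its analysis is described in three places.

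- Preliminary Studies, results and conclusions for vaccination: the vaccine response is kept as a measure because its variability suits "planned within group analyses to determine the correlation between immune function and muscle adaptation to training and detraining".
- Statistical Plan, opening paragraph: "multiple correlation analysis will be used to determine the correlation between endpoints and any possible inflation in the overall Type I error rate". The same paragraph says that this allows "testing of the overall hypothesis that measures of immune function (Aim 1) will be positively correlated with adaptations to exercise" and with retention of the gains (Aim 3). Arm is not mentioned.
- Abstract, Research Plan: "Multivariable testing will then be used to compare the results between Aims 1, 2, and 3". No variables are named.

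The section on other human subject data adds that "medications and medical problems will be recorded and used as potential confounding variables in the statistical or exploratory analyses". Arm is not in that list. All power statements concern differences in means between arms; none gives a power or a detectable r for the correlation.

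**The concern.** An analyst could follow these passages in at least two ways. Taken literally, the vaccination paragraph gives a separate correlation in each arm, each on about 20 people, with no rule for combining the two or for settling a disagreement. The Statistical Plan, read on its own, could be taken as a single correlation over everyone with no term for arm. The first route costs precision. The second can produce a correlation from the treatment itself: if the supplement moves both the immune and the muscle measure, subjects on supplement sit together at one end of both scales, and a pooled correlation appears even if immune function has no bearing on muscle response. The trial wants to read this correlation as evidence about mechanism, so the choice of model matters.

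**Working it through.** **Inputs from the protocol.** N=50 with 20% dropout, at least 20 per group, 5% level, effect 0.8 SD. On sidedness: "Power calculations were based on using a one-sided t-test to compare independent groups". The one-to-one ratio is implied by 20 per group, not stated. The preliminary correlations (R > 0.7) come from 8 subjects (Finding 4).

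**Inputs assumed here.** True r of 0.4 or 0.5, supplement shifts other than 0.8 SD, and a one-sided 5% test of the correlation, carried over from the group comparisons.

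**The plan's own figure.** Power = Φ(0.8 × √(20/2) − 1.645) = Φ(0.885) = 81%; the exact noncentral t with 38 df gives 79.9%. And 40/(1 − 0.2) = 50. The stated 80% is reproduced as a one-sided figure.

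**Precision.** Fisher z with standard error 1/√(n − 3 − k), where k is the number of covariates.

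Detectable r at 80% power = tanh[(1.645 + 0.842)/√(n − 3 − k)]; two-sided, 1.960 replaces 1.645.

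Power = Φ(atanh(r) × √(n − 3 − k) − 1.645), with atanh(0.4) = 0.4236.

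| Analysis | √(n − 3 − k) | Detectable r, one-sided (two-sided) | Power at r=0.4, one-sided (two-sided) |
|---|---|---|---|
| One arm, n=20 | √17 = 4.12 | 0.54 (0.59) | 54% (42%) |
| All, n=40, arm | √36 = 6.00 | 0.39 (0.44) | 82% (72%) |
| All, n=40, arm and baseline muscle value | √35 = 5.92 | 0.40 (0.44) | 81% (71%) |

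At r=0.5 the one-sided powers are 73% (one arm) and 95% (all 40, arm in the model). At r=0.7 one arm of 20 already has 97% one-sided and 95% two-sided. Without dropout, one arm of 25 detects r=0.49 one-sided, against 0.35 for all 50 with arm.

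**Unadjusted pooling.** With equal arms, no within-arm association, and shifts d1 and d2 in SD units, the induced correlation is (d1·d2/4)/√[(1 + d1²/4)(1 + d2²/4)]. For 0.8 in both this is 0.16/1.16 = 0.138; for 0.4 in both, 0.04/1.04 = 0.038. Rejection rates for the one-sided 5% test of a positive correlation, simulated with 20 per arm:

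| Supplement shift (immune, muscle) | False positives, arm omitted |
|---|---|
| 0.8, 0.8 | 22% |
| 0.8, 0.4 | 12% |
| 0.4, 0.4 | 8% |
| 0.8, 0 | 5% |
| −0.8, 0.8 | 0.6% |

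Two-sided, the 0.8/0.8 rate is 14%. With arm in the model, the rate is about 5% in each same-direction and single-measure case simulated (0.8/0.8, 0.4/0.4 and 0.8/0).

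**Interaction check.** With 20 per arm, the difference between two Fisher z values has standard error √(2/17) = 0.343. Two-sided power to separate r=0 from r=0.4 is about 24%, and 80% power needs roughly 0 against 0.74.

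**The case against.** Several counter-arguments have force.

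- **A reader might infer that the plan prescribes unadjusted pooling.** It does not. The Statistical Plan is silent on arm, the only explicit wording points to within-group analysis, and the terms multivariable and multiple correlation suggest a model with more than one term. The pooling scenario shows what the silence permits and no more.
- **A reader might infer that the plan commits to two separate tests on 20 subjects.** The vaccination paragraph gives no n, and its wording could mean a pooled within-group correlation, which is the arm-adjusted partial correlation recommended here. If so, the plan only needs to say it.
- **It would be too strong to say that half the data are thrown away.** Separate correlations in both arms use everyone; the two estimates are simply never combined.
- **Nor is the correlation underpowered at any plausible size.** At the preliminary r of 0.7, 20 subjects are enough. That figure rests on 8 people and is probably optimistic, so it does not settle the matter; the loss bites at r of about 0.3 to 0.5.
- **The 22% is a high-end case.** Some immune measures, such as resting cytokines and NFkB activity, are predicted to fall with supplement. Uncoded, these would push the one-sided error below 5%. The protocol also doubts that its sample will show an arm difference in vaccine response.
- **Slopes may differ by arm**, since the supplement is meant to change immune state. This is a fair reason to keep within-arm estimates in view.

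The vaccination paragraph also mentions a pitfalls section of the proposal, which is not among the documents reviewed and may say more.

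**Conclusion.** The concern holds as an unresolved choice of model for the stated overall hypothesis, for which a better option is available at almost no cost. Against separate within-arm correlations, one arm-adjusted analysis lowers the detectable r from about 0.54 to about 0.39 to 0.40 (from 0.49 to 0.35 without dropout) and, at an assumed true r of 0.4, raises one-sided power from 54% to about 81% (two-sided, 42% to about 71%). It also closes off the unadjusted reading, whose one-sided error would range from under 1% to about 22% over the scenarios examined, depending on the size and direction of the supplement's effects. These figures assume 20 completers per arm, a common slope and approximately normal measures. Adjusting for arm does not remove confounding by age, sex or medication. The randomised comparisons between arms are unaffected.

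**What to change.** State in the Statistical Plan that each immune-muscle association is estimated once, in all subjects, by regressing the muscle outcome on the immune measure with arm and baseline muscle value as covariates, and that the partial correlation is reported with a confidence interval. Specify the expected direction for each immune measure, so that a positive association means the same thing throughout. Report the within-arm correlations and the arm-by-immune interaction descriptively. Bring the vaccination paragraph and the Abstract into line.

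This is a change of wording only, with no added subjects, visits or assays. The two covariates cost two degrees of freedom. The real price is the common-slope assumption: if slopes differ, the model estimates an average, and the interaction test has limited power to reveal it at this sample size. That is why the within-arm estimates should still be shown.
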